5.2 Trial Treatments

The treatment to be used in this trial is outlined below in Table 2

Table 2 Trial Treatment

Drug	Dose/ Potency	Dose Frequency	Route of Administration	Regimen/ Treatment Period	Use
Pembrolizumab	200 mg	Q3W	IV infusion	Day 1 of each 3 week cycle	Experimenta l

Trial treatment should begin on the day of registration or as close as possible to the date on which treatment is available.

5.2.1 Dose Selection/Modification

5.2.1.1 Dose Selection

The rationale for selection of doses to be used in this trial is provided in Section 4.0 – Background and Rationale.

Details on preparation and administration of pembrolizumab (MK-3475) are provided in the Pharmacy Manual.

5.2.1.2 Dose Modification

Adverse events (both non-serious and serious) associated with pembrolizumab exposure may represent an immunologic etiology. These adverse events may occur shortly after the first dose or several months after the last dose of treatment. Pembrolizumab must be withheld for drug-related toxicities and severe or life-threatening AEs as per Table 3 below. See Section 5.6.1 and Events of Clinical Interest Guidance Document for supportive care guidelines,

including use of corticosteroids. Although leukopenia, anemia, and thrombocytopenia are expected as a natural consequence of the disease being treated and will be present at baseline for the majority of enrolled subjects, grade 4 treatment emergent hematologic toxicity will require drug treatment interruption regardless of attribution and can be re-started once the hematologic toxicity has resolved to baseline or at least grade 3. Treatment emergent grade 3/4 anemia and thrombocytopenia will be managed with red blood cell and platelet transfusional support as pre treating investigators discretion.

Table 3. Dose Modification Guidelines for Drug-Related Adverse Events

Toxicity	Hold Treatment For Grade	Timing for Restarting Treatment	Discontinue Subject
Diarrhea/Colitis	2-3	Toxicity resolves to Grade 0-1.	Toxicity does not resolve within 3 weeks of last dose or inability to reduce corticosteroid to 10 mg or less of prednisone or equivalent per day within 12 weeks.
	4	Permanently discontinue	Permanently discontinue
AST, ALT, or Increased Bilirubin	2	Toxicity resolves to Grade 0-1	Toxicity does not resolve within 3 weeks of last dose.
	3-4	Permanently discontinue (see exception below) ¹	Permanently discontinue
Type 1 diabetes mellitus (if new onset) or Hyperglycemia	T1DM or 3-4	Hold pembrolizumab for new onset Type 1 diabetes mellitus or Grade 3-4 hyperglycemia associated with evidence of beta cell failure.	Resume pembrolizumab when patients are clinically and metabolically stable.
Hypophysitis	2	Toxicity resolves to Grade 0-1	Toxicity does not resolve within 3 weeks of last dose or inability to reduce corticosteroid to 10 mg or less of prednisone or equivalent per day within 12 weeks.
	3-4	Permanently discontinue	Permanently discontinue

Toxicity	Hold Treatment For Grade	Timing for Restarting Treatment	Discontinue Subject
Hyperthyroidism	2	Toxicity resolves to Grade 0-1	Toxicity does not resolve within 3 weeks of last dose or inability to reduce corticosteroid to 10 mg or less of prednisone or equivalent per day within 3 weeks.
	3-4	Permanently discontinue	Permanently discontinue
Hypothyroidism	2-4	Therapy with pembrolizumab can be continued while treatment for the thyroid disorder is instituted	Therapy with pembrolizumab can be continued while treatment for the thyroid disorder is instituted.
Infusion Reaction	3-4	Permanently discontinue	Permanently discontinue
Pneumonitis	2	Toxicity resolves to Grade 0-1	Toxicity does not resolve within 3 weeks of last dose or inability to reduce corticosteroid to 10 mg or less of prednisone or equivalent per day within 3 weeks.
	3-4	Permanently discontinue	Permanently discontinue
Renal Failure or Nephritis	2	Toxicity resolves to Grade 0-1	Toxicity does not resolve within 3 weeks of last dose or inability to reduce corticosteroid to 10 mg or less of prednisone or equivalent per day within 3 weeks.
	3-4	Permanently discontinue	Permanently discontinue
All Other Drug-	2	Toxicity resolves to Grade 0-1	Toxicity does not resolve within 3 weeks of last dose or inability to reduce

Toxicity	Hold Treatment For Grade	Timing for Restarting Treatment	Discontinue Subject
Related Toxicity ²			corticosteroid to 10 mg or less of prednisone or equivalent per day within 3 weeks.
	3-4	Permanently discontinue	Permanently discontinue

Note: Permanently discontinue for any severe or Grade 3 drug-related AE that recurs or any life-threatening event.

¹ For patients with liver metastasis who begin treatment with Grade 2 AST or ALT, if AST or ALT increases by greater than or equal to 50% relative to baseline and lasts for at least 1 week then patients should be discontinued.

² Patients with intolerable or persistent Grade 2 drug-related AE may hold study medication at physician discretion. Permanently discontinue study drug for persistent Grade 2 adverse reactions for which treatment with study drug has been held, that do not recover to Grade 0-1 within 3 weeks of the last dose.

Dosing interruptions are permitted in the case of medical / surgical events or logistical reasons not related to study therapy (e.g., elective surgery, unrelated medical events, patient vacation, and/or holidays). Subjects should be placed back on study therapy within 3 weeks of the scheduled interruption, unless otherwise discussed with the Sponsor. The reason for interruption should be documented in the patient's study record.

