11.3 Safety Stopping Rules

Sponsor and DBMB will meet quarterly to review the patient data for safety as related to the stopping rules as defined in this section.

If a patient experiences grade 3 or higher toxicities (excluding grade 3/4 hematologic toxicity) deemed at least possibly related to the study drug (and not clearly disease related), or if grade 2 laboratory (excluding grade 2 hematologic toxicity) or clinical toxicities deemed at least possibly related to the study drug (and not clearly disease related) do not resolve within 3 weeks in spite of treatment, we will stop study drug administration.

If, among the MF-CP (primary cohort) patients, 3 or more of the first 5, 4 or more of the first 10, 6 or more of the first 15, or 7 or more of the first 24 patients stop study drug within the first 3 cycles due to toxicity as defined above in the previous paragraph, we will stop

Product: MK-3475

Protocol/Amendment No.:

enrolling patients to the primary cohort. The probability of stopping early if the true toxicity rate is 20%, 30%, 40% or 45% is 0.18, 0.51, 0.81, 0.91, respectively.

If, among the MPN-AP/BP (exploratory cohort) patients, 2 or more of the first 5 or 3 or more of the first 10 patients, stop study drug within the first 3 cycles [due to toxicity as defined above in the previous paragraph](#), we will stop enrolling patients to the exploratory cohort. The probability of stopping early if the true toxicity rate is 20%, 30%, 40% or 50% is 0.26, 0.48, 0.66, 0.81, respectively.

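### Section 5.2.1.2 gives opposite stop-or-restart instructions for drug-related Grade 4 hematologic toxicity: the body text allows restart at Grade 3, while Table 3 ends treatment

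*Combined protocol and SAP*

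**What the plan says.** Four places in the combined protocol and SAP bear on this.

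- **Section 5.2.1.2, body text.** For Grade 4 events, "grade 4 treatment emergent hematologic toxicity will require drug treatment interruption regardless of attribution and can be re-started once the hematologic toxicity has resolved". The restart level is given as "once the hematologic toxicity has resolved to baseline or at least grade 3". A further sentence says "Treatment emergent grade 3/4 anemia and thrombocytopenia will be managed with red blood cell and platelet transfusional support", at the investigator's discretion. The paragraph also notes that leukopenia, anemia and thrombocytopenia "will be present at baseline for the majority of enrolled subjects".
- **Section 5.2.1.2, Table 3 and its Note.** The body text makes the table mandatory: "Pembrolizumab must be withheld for drug-related toxicities and severe or life-threatening AEs as per Table 3 below". The title is "Table 3. Dose Modification Guidelines for Drug-Related Adverse Events". No row covers hematologic events, and neither the title, the Note nor the footnotes exclude them. The catch-all row for other drug-related toxicity ends treatment permanently at Grade 3-4. The Note reads "Permanently discontinue for any severe or Grade 3 drug-related AE that recurs or any life-threatening event".
- **Section 11.3.** The rule for stopping drug in an individual patient applies to possibly related toxicity of Grade 3 or higher, "excluding grade 3/4 hematologic toxicity". It also leaves out Grade 2 hematologic toxicity from its rule on unresolved Grade 2 events.
- **Section 5.8.** Discontinuation is required for unacceptable adverse experiences as set out in Section 5.2.1.2, so the reader is sent back to the same section.

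**The concern.** The body text and Table 3 cover the same event and prescribe different actions. Because the body text applies whatever the attribution, it cannot be confined to cytopenias unrelated to the drug. A drug-related Grade 4 cytopenia is therefore covered by a rule that lets the patient restart and by another that removes the patient from treatment for good.

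Three centers enrol patients, and each could follow the protocol exactly and still treat identical patients differently. Either action could then be cited as a departure from the other provision. The choice bears on safety and on the analysis. The primary endpoint is response after 6 cycles, the per-protocol set requires 6 completed cycles (Section 8.1.1.1), and the interim analysis assesses a patient who withdraws early at withdrawal, not after cycle 6 (Section 8.3). Entry is allowed at an absolute neutrophil count of 500 and platelets of 25,000 (Table 1), so the protocol knowingly admits patients with low counts.

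**Working it through.** The plan states no figure on this point, so there is none to reproduce. The check is a comparison of the provisions, case by case.

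| Event | Body text of 5.2.1.2 | Table 3 catch-all row | Table 3 Note | 11.3 patient-level rule |
|---|---|---|---|---|
| Drug-related Grade 4 cytopenia, back to Grade 3 or baseline | Interrupted; may restart | Treatment ended | Treatment ended, if Grade 4 counts as life-threatening | Not a trigger |
| Drug-related Grade 3 cytopenia, first occurrence | No interruption required; Grade 3 is an accepted restart level | Treatment ended | Not reached | Not a trigger |
| Drug-related Grade 3 cytopenia, recurring | As above | Treatment ended | Treatment ended | Not a trigger |
| Unrelated Grade 4 cytopenia | Interrupted; may restart | Does not apply | Unclear: the life-threatening clause is not worded as drug-related, but the table's title is | Not a trigger |

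1. **Grade 4, drug-related.** The conflict is direct. Permission to restart and permanent discontinuation cannot both apply to one patient.
2. **The Note at Grade 4.** Table 10 describes Grade 4 as involving life-threatening consequences, which brings Grade 4 cytopenia within the Note. Under seriousness, the same table defines life-threatening more narrowly, as immediate risk of death from the event as it occurred. The Note does not say which sense it uses. The conflict with the catch-all row does not depend on this.
3. **Grade 3, drug-related.** The conflict is between the restart threshold, which accepts dosing at Grade 3, and the catch-all row, which ends treatment at Grade 3. The Note reaches Grade 3 only on recurrence. For neutropenia and leukopenia at Grade 3 the body text gives no action beyond that threshold.
4. **Section 11.3.** It writes its hematologic exclusion out; Table 3 does not. Section 11.3 therefore agrees with the body text and disagrees with the table.

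**How many patients.** The documents give no rate of drug-related Grade 3-4 cytopenia. Let h be an assumed share of primary-cohort patients who have one. The expected number among 24 is 24h, and the chance of at least one is 1 - (1 - h)^24.

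| Assumed h | 24h | Chance of at least one |
|---|---|---|
| 5% | 1.2 | 1 - 0.95^24 = 0.71 |
| 10% | 2.4 | 1 - 0.90^24 = 0.92 |
| 20% | 4.8 | 1 - 0.80^24 = 0.995 |
| 30% | 7.2 | 1 - 0.70^24 > 0.99 |

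These rates are assumptions that span a range; they are not estimates.

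**The case against.** The best defense is that the hematologic wording in the body text is specific, is explicit about attribution, and is echoed by Section 11.3, so it should be read as overriding a generic row. As a guess at the drafters' intent this is plausible, and it stands to that extent: two of the three provisions point the same way. It does not remove the contradiction, because no provision states precedence and the same paragraph makes Table 3 mandatory.

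Several stronger readings are tempting, but the documents do not support them.

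- *Most patients are affected.* The statement about the majority concerns cytopenia at baseline. The conflict needs an event that is treatment-emergent, Grade 3-4 and drug-related.
- *The trial loses a calculable amount of power.* Nothing says what share of responders would be stopped. Table 5 also denies clinical improvement where anemia, thrombocytopenia or neutropenia has become more severe, so patients whose cytopenia stays worse would largely fail the endpoint under either rule.
- *The transfusion sentence itself contradicts the table.* Transfusion is supportive care and is compatible with stopping the drug.
- *The hold limits conflict, or a patient with Grade 2 anemia at baseline can never restart.* The 3-week limit and the Grade 0-1 restart condition belong to the row's Grade 2 line, while the body text's hold concerns Grade 4. Under Section 7.2 a pre-existing condition becomes an adverse event only if it worsens.
- *Monitoring could not see the problem.* The cohort rule in Section 11.3 does omit these events. But Section 11.1 has adverse event rates, out-of-range laboratory values and adherence to the intervention reviewed quarterly, and Table 10 has sites record whether an event led to discontinuation.

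**Conclusion.** The point holds in a limited form. Section 5.2.1.2 contradicts itself for drug-related Grade 4 hematologic toxicity. At Grade 3 it is inconsistent between the restart threshold and the catch-all row. Section 11.3 disagrees with Table 3, and Section 5.8 refers back without settling the matter.

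This conclusion rests on the wording alone. It assumes only that a cytopenia judged drug-related is a drug-related toxicity within the catch-all row, since no other row fits and none excludes it. The number of patients concerned is unknown. Under the assumed rates of 5% to 30%, between 1.2 and 7.2 of 24 would be expected to have an event in the disputed range. No effect on power or error rates is claimed. The matter still needs correcting, because sites following the plan exactly face opposite instructions on whether the same patient stays on drug.

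**What to change.** Reconcile the body text of Section 5.2.1.2, the Table 3 catch-all row, the Table 3 Note and Section 11.3, and state in each which provision governs hematologic toxicity. The amendment should settle:

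- whether hematologic events fall inside or outside the catch-all row, for example by an explicit hematologic row or a stated exclusion;
- the restart condition, including whether dosing at Grade 3 is accepted;
- whether the Note applies to Grade 4 cytopenia, in which sense it uses life-threatening, and whether that clause is limited to drug-related events;
- what applies to Grade 3 neutropenia and leukopenia, for which the body text gives no action of its own.

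Which rule is clinically right is for the sponsor to decide. The cost is a wording amendment, with no added patients, visits or tests.

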 - For **Grade 3 or 4 diarrhea/colitis** that persists > 1 week, treat with intravenous steroids followed by high dose oral steroids.
 - When symptoms improve to Grade 1 or less, steroid taper should be started and continued over no less than 4 weeks.
- **Type 1 diabetes mellitus (if new onset, including diabetic ketoacidosis [DKA]) or ≥ Grade 3 Hyperglycemia, if associated with ketosis (ketonuria) or metabolic acidosis (DKA)**
 - For **T1DM** or **Grade 3-4 Hyperglycemia**
 - Insulin replacement therapy is recommended for Type I diabetes mellitus and for Grade 3-4 hyperglycemia associated with metabolic acidosis or ketonuria.
 - Evaluate patients with serum glucose and a metabolic panel, urine ketones, glycosylated hemoglobin, and C-peptide.
- **Hypophysitis:**
 - For **Grade 2** events, treat with corticosteroids. When symptoms improve to Grade 1 or less, steroid taper should be started and continued over no less than 4 weeks. Replacement of appropriate hormones may be required as the steroid dose is tapered.
 - For **Grade 3-4** events, treat with an initial dose of IV corticosteroids followed by oral corticosteroids. When symptoms improve to Grade 1 or less, steroid taper should be started and continued over no less than 4 weeks. Replacement of appropriate hormones may be required as the steroid dose is tapered.
- **Hyperthyroidism or Hypothyroidism:**

Thyroid disorders can occur at any time during treatment. Monitor patients for changes in thyroid function (at the start of treatment, periodically during treatment, and as indicated based on clinical evaluation) and for clinical signs and symptoms of thyroid disorders.

 - **Grade 2** hyperthyroidism events (and **Grade 2-4** hypothyroidism):
 - In hyperthyroidism, non-selective beta-blockers (e.g. propranolol) are suggested as initial therapy.
 - In hypothyroidism, thyroid hormone replacement therapy, with levothyroxine or liothyronine, is indicated per standard of care.
 - **Grade 3-4** hyperthyroidism
 - Treat with an initial dose of IV corticosteroid followed by oral corticosteroids. When symptoms improve to Grade 1 or less, steroid

taper should be started and continued over no less than 4 weeks. Replacement of appropriate hormones may be required as the steroid dose is tapered.

- **Hepatic:**
 - For **Grade 2** events, monitor liver function tests more frequently until returned to baseline values (consider weekly).
 - Treat with IV or oral corticosteroids

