7.1.5.2 Treatment Period

The treatment period will consist of 3 week cycles in which the study drug will be given on day 1 of each cycle and the following tests and procedures will be obtained: prior con med review, adverse event review, physical exam with attention to spleen length in craniocaudal direction measured by a ruler at the mid clavicular line from the costal margin, vitals, ECOG, CBC and comprehensive serum chemistry, and thyroid function tests (on C3D1).

The core study period is a total of 6 cycles (study visits and drug administration will take place on day 1 of each cycle and the window is +/- days). Response assessment visit will take place on cycle 7 day 1 which will include the addition of a bone marrow biopsy and aspiration and biomarker evaluation from the aspirate and peripheral blood. The PI will decide if the subject will continue receiving therapy in the extension phase (Cycle 7+) of the trial as long the following is true: at least a clinical improvement by IWG-ELN criteria (Table 5) for chronic phase patients and at least a partial response by Table 6A and 6B (secondary objective) for accelerated and blast phase patients; the absence of unacceptable toxicity; both patient and treating physician are in favor of continued treatment on protocol. Patients can continue receiving study drug in the extension phase as long as they do not meet criteria for discontinuation of treatment defined in Section 5.8 and to a maximum duration of 2 years

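### Section 11.3 stops pembrolizumab for Grade 3 hypothyroidism that Table 3 lets patients be treated through, and does not say whether a hold counts as a stop

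*Combined protocol and SAP*

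**What the plan says.** Three parts of the protocol decide what happens when a patient has a drug-related toxicity.

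- **Section 5.2.1.2, Table 3.** The hypothyroidism row covers Grades 2 to 4. Both its restart and its discontinuation columns read "Therapy with pembrolizumab can be continued while treatment for the thyroid disorder is instituted". Two other rows also keep a Grade 3 patient eligible for more drug. Hyperglycemia with beta cell failure is held and resumed once the patient is stable. Diarrhea/colitis of Grade 2 or 3 is held and restarted when it falls to Grade 0-1. A Note under the table adds: "Permanently discontinue for any severe or Grade 3 drug-related AE that recurs or any life-threatening event".
- **Section 5.6.1, Supportive Care Guidelines.** For Grade 2-4 hypothyroidism: "In hypothyroidism, thyroid hormone replacement therapy, with levothyroxine or liothyronine, is indicated per standard of care".
- **Section 11.3, Safety Stopping Rules.** This section gives its own patient-level instruction. The first trigger begins "If a patient experiences grade 3 or higher toxicities (excluding grade 3/4 hematologic toxicity) deemed at least possibly related to the study drug", provided the event is not clearly due to the disease. The second covers Grade 2 toxicities that "do not resolve within 3 weeks in spite of treatment, we will stop study drug administration". Hematologic toxicity is the only type exempted. Enrolment to the primary cohort then ends at 3 stops in 5 patients, 4 in 10 or 6 in 15. The last primary boundary is "7 or more of the first 24 patients stop study drug within the first 3 cycles due to toxicity as defined above". The exploratory cohort ends at "2 or more of the first 5 or 3 or more of the first 10 patients, stop study drug within the first 3 cycles".

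Sections 5.6.1 and 5.8 refer the reader to Section 5.2.1 and Section 5.2.1.2 for dose modification and unacceptable toxicity. Neither mentions Section 11.3, and Section 11.3 does not mention Table 3.

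**The concern.** A safety rule that counts patients who stop drug needs one definition of stopping. Here the count depends on which section the site follows. A patient with Grade 3 hypothyroidism kept on drug under Table 3 is not counted. The same patient taken off drug under Section 11.3 is counted if this happens in the first 3 cycles. With three centers, both readings could be applied within one cohort.

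Two things are at stake. One is the patient's treatment, which one section allows to continue and the other ends. The other is a consistent tally against boundaries of only a few patients. The sponsor and the data and safety monitoring board review these rules quarterly, but the rule they apply carries the same ambiguity.

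**Working it through.** The point is textual, so the first step sets the instructions side by side for a first, drug-related, non-hematologic event.

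| Event | Table 3 | Section 11.3 | Counted, if in the first 3 cycles? |
|---|---|---|---|
| Grade 3 hypothyroidism | May continue on replacement | Stop | Yes under 11.3, no under Table 3 |
| Grade 2 hypothyroidism unresolved after 3 weeks of treatment | May continue on replacement | Stop | Yes under 11.3, no under Table 3 |
| Grade 3 diarrhea/colitis | Hold, then restart | Stop, not defined as temporary or permanent | Not stated |
| Grade 3 hyperglycemia with beta cell failure | Hold, then resume | Stop, not defined as temporary or permanent | Not stated |
| Grade 3 hepatic (subject to its footnote), hypophysitis, hyperthyroidism, infusion reaction, pneumonitis, renal, all other | Permanent discontinuation | Stop | Yes under both |

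The first two rows conflict. The next two turn on an undefined word. In the last row the sections agree, so the problem is confined to three rows of Table 3.

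**Can such a case fall inside the counting window?**
- Window: 3 cycles × 21 days = days 1 to 63.
- Section 7.1.5.2 schedules "CBC and comprehensive serum chemistry, and thyroid function tests (on C3D1"). Nominal C3D1 is 2 × 21 + 1 = day 43, inside the window.
- Grade 3: Section 11.3 sets no waiting period, so a case found then, or clinically at any earlier visit, can count.
- Grade 2: the 3-week period must also run. From day 43 it ends on day 43 + 21 = 64. Section 5.2.2 lets dosing move 3 days either way, and Section 7.1.3 lets pre-dose labs be drawn up to 72 hours before dosing. The sample can therefore fall between day 43 − 3 − 3 = 37 and day 43 + 3 = 46, and the 3 weeks end between day 58 and day 67. That range straddles day 63, so a Grade 2 case may or may not be counted.

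**Where could one patient change the outcome?** Only where the count is otherwise one short of a boundary:
- Primary: 3 − 1 = 2 of the first 5; 4 − 1 = 3 of the first 10; 6 − 1 = 5 of the first 15.
- Exploratory: 2 − 1 = 1 of the first 5.
- The last boundaries fall at 24 (9 + 15) and 10, which are the full cohort sizes, so little enrolment is left to stop.

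**The plan's own figures.** Section 11.3 prints stopping probabilities of 0.18, 0.51, 0.81 and 0.91 for the primary cohort at true toxicity rates of 20%, 30%, 40% and 45%. An exact sequential binomial calculation with all four boundaries as written gives 0.247, 0.658, 0.919 and 0.970, so the printed figures are not reproduced. That is a separate matter, and nothing here depends on it.

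**The case against.** The best defence is that Table 3 is headed as guidelines and only permits continuation, while Section 11.3 is mandatory. A site that stops drug breaches nothing in Table 3. That much is true, but it does not reconcile the sections, because a site that uses the permission breaches Section 11.3. The cross-references in Sections 5.6.1 and 5.8 lead sites to Table 3, so following it is a reasonable reading.

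The second defence is that other safeguards exist. Section 11.1 sends all adverse events and rates to the sponsor and the board quarterly and has serious events reviewed as they occur. Section 5.10 allows termination on the incidence or severity of drug reactions, whatever the count. This stands: an uncounted event would still be seen. It limits the harm but does not make the count consistent.

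Several stronger readings are tempting but not supported:
- A reader might infer that the Table 3 Note also contradicts the hypothyroidism row at Grade 4. That depends on equating Grade 4 with life-threatening. Table 10's grade description suggests this, but its narrower seriousness definition requires immediate risk of death. The Note can also be read as overriding the rows.
- A reader might infer that the diarrhea/colitis and hyperglycemia rows contradict Section 11.3 outright. They do only if stop means permanent, which Section 11.3 does not say.
- A reader might infer a definite rise in the chance of halting a cohort. The documents give no rate for these events. One patient's share of a boundary, such as 1 of 3, would be the same for any misclassified patient and does not measure this defect.

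**Conclusion.** The plan is wrong as written for drug-related Grade 3 hypothyroidism and for Grade 2 hypothyroidism unresolved after 3 weeks: two sections give incompatible rules and neither is ranked. For Grade 3 diarrhea/colitis and Grade 3 hyperglycemia with beta cell failure, the defect is the narrower one of an undefined term.

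The size is modest. Few events are expected. The response-rate design, its alpha and power, and the sample size do not change. What is affected is the dosing of individual patients and whether the same event is always counted the same way. This assumes that the event is judged at least possibly related and not clearly disease related, and that a counted stop falls in the first 3 cycles. It is a minor to moderate fault that should be corrected because the correction is cheap.

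**What to change.** Add to Section 11.3, stated to prevail over its patient-level paragraph where they differ:

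*Individual dosing follows Table 3, including its Note on recurrent Grade 3 and life-threatening events. Hypothyroidism continued on hormone replacement under Table 3 is not a stop. For the boundaries, a stop is a permanent discontinuation for toxicity required by Table 3 within the first 3 cycles; a hold followed by restart under Table 3 does not count.*

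Leave the Table 3 Note and the diarrhea/colitis row as they are. Exempting diabetes or hyperglycemia from the Note would be a clinical change, since Section 5.6.1 places diabetic ketoacidosis under that heading. Making Grade 3 colitis a permanent discontinuation would be another. Neither is needed to remove the conflict.

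The cost is three sentences. Boundary numbers, sample size and analysis stay the same, but the counted event is now defined and slightly fewer events will count. For example, a hold begun in cycle 3 that becomes permanent in cycle 4 would fall outside the tally. Held events remain visible in the quarterly adverse event review by the sponsor and the board.
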